### **8.1.11 Review of results**

Review of ECG results, eye examination report, laboratory reports, data entered in the diaries etc. must be documented either on the documents, printouts, or in the subject's medical record. The documents must be retained at the site as source documentation.

If it is needed to clarify entries or discrepancies in the diary, the subject must be questioned and a conclusion made in the subject's medical record. Care must be taken not to bias the subject. Any discrepancies or missing data points available elsewhere related to a 7-9-7 point profile or hypoglycaemic episodes must be corrected or added.

For ECGs, physical examinations and eye examinations, the evaluations must follow the categories:

- Normal
- Abnormal
  - Was the result clinically significant? (yes/no)

The evaluation should be based on investigator's judgement.

For laboratory report values outside the reference range, the investigator must specify whether the value is clinically significant or not clinically significant. Review of laboratory reports must be documented either on the documents and/or in the subject's medical record.

## **8.2 Subject related information/assessments**

### **8.2.1 Demography**

Demography will be recorded at screening and consists of:

- Date of birth (according to local regulation)
- Sex
- Ethnicity (according to local regulation)
- Race (according to local regulation)

## 8.2.2 Diabetes history

Diabetes history will be recorded at screening and consists of:

- Date of diagnosis of T1DM or T2DM

## 8.2.3 Hypoglycaemia unawareness

Information on hypoglycaemia unawareness will be recorded at screening according to Clarke's questionnaire, question 8.

The investigator must ask the subject whether he/she has ever experienced a hypoglycaemic episode? If the subject answers "yes", the investigator must ask the subject in the following way: "To what extent can you tell by your symptoms that your blood glucose is low?" The subject can answer never, rarely, sometimes, often or always.

Subjects answering 'never, rarely or sometimes' are considered as having impaired awareness of hypoglycaemia.

## 8.2.4 Concomitant illness and medical history

A **concomitant illness** is any illness that is present at the start of the trial (V1) or found as a result of a screening procedure or other trial procedures performed before exposure to trial product.

Date of diagnosis of T1DM or T2DM should be reported separately in the Diabetes History Form in the eCRF.

**Medical history** is a medical event that the subject has experienced in the past. Only relevant medical history, as judged by the investigator, should be reported.

The information collected for concomitant illness and medical history should include diagnosis, date of onset and date of resolution or continuation, as applicable.

Diabetes complications will be recorded at screening as part of the Concomitant illness and medical history and consists of;

Information regarding diabetes complications including date of onset:

- Diabetic retinopathy
- Diabetic neuropathy
- Diabetic nephropathy
- Macroangiopathy (including peripheral vascular disease)

Any change to a concomitant illness should be recorded during the trial. A clinically significant worsening of a concomitant illness must be reported as an AE (Section 12.2).

Protocol  
Trial ID: NN1218-4357  
UTN: U1111-1197-8289

CONFIDENTIAL

Date:  
Version:  
Status:  
Page:

30 November 2020  
5.0  
Final  
44 of 105

Novo Nordisk

It must be possible to verify the subject's medical history in source documents such as subject's medical record. If a subject is not from the investigators own practice; the investigator must make reasonable effort to obtain a copy of subject's medical record from relevant party e.g. primary physician. The investigator must document any attempt to obtain external medical information by noting the date(s) when information was requested and who has been contacted.

### 8.2.5 Concomitant medication

A **concomitant medication** is any medication, other than the trial product(s), which is taken during the trial, including the screening, run-in, treatment and follow-up periods.

Details of any concomitant medication must be recorded at V1. Changes in concomitant medication must be recorded at each visit as they occur.

The information collected for each concomitant medication includes:

- trade name or generic name
- indication
- start date and stop date or continuation

If a change is due to an AE, then this must be reported according to Section 12. If the change influences the subject's eligibility to continue in the trial, the monitor must be informed.

### 8.2.6 Concomitant medication (diabetes)

Any diabetes medication, other than the trial product(s) which is taken during the trial, including the screening, run-in, treatment and follow-up periods must be recorded in a separate concomitant medication (diabetes) form in the eCRF, including:

- trade name or generic name
- total daily dose
- frequency
- start date and stop date or continuation

For subjects treated with metformin it is the start date and dose of last metformin dose which should be reported.

At the run-in visit (V2), pre-trial insulin(s) and OADs except for metformin for T2DM subjects must be discontinued and a stop date recorded. For T2DM subjects treated with metformin, investigator should at each weekly contact (visit or phone contact), confirm with the subject that dose and frequency of metformin has been unchanged. This should be documented in the medical records.

At the randomisation visit (V10) run-in bolus insulin (NovoRapid®) must be discontinued and a stop date recorded.

### 8.2.7 Childbearing potential

It must be recorded in the eCRF whether female subjects are of childbearing potential.

Pregnancy testing must be performed on female subjects of childbearing potential as described in Section 8.5.2. Female subjects of childbearing potential must be instructed to use adequate contraceptive methods (sterilisation, IUD, oral contraceptives or barrier methods) throughout the trial and until 1 week after end of treatment.

Female of non-childbearing potential is defined as:

- Female who has undergone a hysterectomy, bilateral oophorectomy or bilateral tubal ligation
- Postmenopausal defined as no menses for 12 months without an alternative medical cause
- Other medical reasons preventing childbearing potential

### 8.2.8 Tobacco use

Details of tobacco use must be recorded at V1. Smoking is defined as smoking at least one cigarette or equivalent daily.

Smoking status:

- Never smoked
- Previous smoker, smoking stop date
- Current smoker

## 8.3 Efficacy assessments

### 8.3.1 Meal test

The subject will undergo a standardised liquid meal test at two visits (V10 and V26/V26A) (see flowchart Section 2) and will have their -2, 30, 60, 120 and 180 minutes PPG measured. The total duration of the meal test is expected to be up to 5 hours including preparations. During that time blood samples will be drawn for plasma glucose, as specified in Table 8-1.

Protocol  
Trial ID: NN1218-4357  
UTN: U1111-1197-8289

CONFIDENTIAL

Date:  
Version:  
Status:  
Page:

30 November 2020  
5.0  
Final  
46 of 105

Novo Nordisk

## Before initiation of the meal test

The subject should be instructed to:

- Follow normal routine regarding eating and exercise habits on the day prior to the meal test
- Refrain from intake of alcohol and use of medications that affect motility (i.e. prokinetics, anticholinergics, tricyclic antidepressants) on the day prior to the meal test, unless the subject was on this medication at trial entry and does not change the product or product dose
- Remember to bring their current/trial bolus and basal insulins, diary and BG meter to the meal test visits
- Attend the meal test visits in a fasting condition. For definition of fasting, please refer to Section 8.1.5. If subjects are normally dosing basal insulin in the morning, as well as metformin dosing in the morning, it is important they wait until after completion of the meal test
- Achieve an SMPG value within a range of 4.0-8.8 mmol/L [71-160 mg/dL] before beginning the meal test. The SMPG value should be verified at the site before starting the meal test

The meal test should be re-scheduled within the visit window and at V10 before randomisation to trial product in case:

- Any hypoglycaemic episode occurs from midnight before the meal test
- The subject is not fasting or
- The SMPG value is outside the range

At V10 (randomisation visit) the investigator must evaluate if the subject is eligible to continue in the trial before the meal test is performed. Only subjects eligible for randomisation should have the V10 meal test performed. Thus, this assessment should not be performed for run-in failure subjects. Randomisation should not take place before the meal test has ended.

## Bolus insulin dose and meal test carbohydrate amount

The standardised liquid meal will be provided by Novo Nordisk and contains approximately 90 grams of carbohydrates. The volume of the liquid meal to be consumed should be measured out by the investigator to be the equivalent to approximately 90 grams of carbohydrates.

The bolus insulin dose should be calculated by the investigator based on the dose level of 0.2 unit/kg body weight. Body weight must be measured prior to the meal test. The calculated dose should be rounded to the nearest whole unit. The 0.2 unit/kg dose is chosen as an approximation of a clinically relevant bolus dose needed for the given size of a standardised meal.

The insulin should be administered subcutaneously in the abdomen in accordance with [Table 8-1](#).

## Initiation of meal test

The subject's body weight must be measured before start and a blood sample must be drawn two minutes before intake of the standardised meal.

Protocol  
Trial ID: NN1218-4357  
UTN: U1111-1197-8289

~~CONFIDENTIAL~~

Date: 30 November 2020 | **Novo Nordisk**  
Version: 5.0  
Status: Final  
Page: 47 of 105

For the meal test at V10 the subject must receive the bolus insulin (NovoRapid®) that was used in the run-in period.

For the meal test at V26 or V26A (for subjects who have prematurely discontinued trial products) the subject should receive the bolus trial insulin they were randomised to and have used throughout the treatment period.

The start of consumption of the liquid meal is defined as time point 0. The subject must consume the liquid meal as quickly as possible and within 12 minutes. The investigator should confirm that the subject consumed the required volume of the standardised liquid meal in the eCRF.

**Table 8–1** Meal test schedule

Time point (minutes)	Blood sample	SMPG values	Standardised meal	Bolus insulin injection
Before start of meal test		X (within target range 4.0-8.8 mmol/L [71-160 mg/dL])		
-2	X			
0			X	X Insulin injection at the start of the meal
15				
30	X	X (as appropriate to ensure subject's safety)		
60	X			
120	X			
180	X			
End of meal test		X (for subject's safety)		

### Conduct of meal test

The subject should stay in the clinic to have the blood samples drawn after -2, 30, 60, 120 and 180 minutes from the start of the standardised meal, as detailed in Table 8–1. The samples will be analysed by the central laboratory.

During the meal test the subject should be resting in a chair. No smoking or intake of food and liquids will be allowed during the meal test, except for water consumption which is allowed from two hours after intake of the standardised meal.

If SMPG values  $\leq 3.9$  mmol/L [70 mg/dL] are measured, then the hypoglycaemia should be treated with glucose rescue treatment according to local practice and the meal test should continue according to the investigator's discretion. The hypoglycaemic episode must be reported. Please see Section 8.4.2.

After the end of the meal test, the investigator should make sure that the subject is safe to leave the site by performing an additional SMPG measurement.

When the meal test at V10 is completed, the subject will be instructed to discontinue NovoRapid® and start treatment with randomised trial product. When the meal test at V26/V26A is completed, the subjects will be switched to a marketed insulin product according to investigator's discretion as detailed in section 8.1.7 and 8.1.9.

## Data collection

The following must be recorded in relation to the meal test:

- Body weight
- Fasting status
- SMPG value measured before the meal test within allowed ranges and the time of the measurement
- Actual clock start and end time of standardised meal
- Volume of meal consumed
- Confirmation that the subject consumed the required volume of the standardised meal
- Batch number of the standardised meal consumed
- Actual clock time and dose of bolus insulin
- Actual clock time of blood samples
- Hypoglycaemic episodes, if relevant
  - SMPG value, time of intervention and amount of glucose rescue treatment and hypoglycaemic episode form

Laboratory results from meal test data will be loaded directly into the trial database by the central laboratory. The meal test results will not be provided to the investigator until after LPLV in order to keep the blinding of the subject and investigator.

### 8.3.2 Self-measured plasma glucose

At V2, subjects will be provided with a BG meter including auxiliaries as well as instructions for use. The subjects will be instructed in how to use the device.

The BG meters use test strips calibrated to plasma values. Therefore, all measurements performed with capillary blood are automatically calibrated to plasma equivalent glucose values, which will be shown on the display.

Protocol  
Trial ID: NN1218-4357  
UTN: U1111-1197-8289

**CONFIDENTIAL**

Date:  
Version:  
Status:  
Page:

30 November 2020  
5.0  
Final  
49 of 105

**Novo Nordisk**

Only the BG meter provided by Novo Nordisk should be used for the measurements required in the protocol.

Subjects must be instructed in how to transfer/record the results of the SMPG values into the diary. For each SMPG value date, time and value will be included.

#### **4-point self-measured plasma glucose profile**

For insulin titration purposes, the subjects will be instructed to perform 4-point profiles in the diary on the three days prior to a scheduled site visit/phone contact every week from V2 to V26, or V26A for subjects who discontinue prematurely. The measurements should be performed at the following time points:

- Before breakfast
- Before lunch
- Before main evening meal (dinner)
- At bedtime

For 4-point SMPG measurements date and value should be transferred to/recorded in the diary, where each measurement should be assigned to the corresponding time point.

SMPG values measured before breakfast, lunch, main evening meal, and at bedtime should be performed before any injection of bolus insulin and just before the start of the meal (breakfast, lunch or main evening meal). SMPG values measured before breakfast should be performed in a fasting condition. The 4-point profile is part of the 7- or 9-point profiles which are measured prior to selected site visits.

#### **7-9-7 point self-measured plasma glucose profile**

The 7- and 9-point SMPG profiles will be used for titration purposes and for efficacy analysis of the trial. The subject will be instructed to perform a 7-9-7 point profile on the 3 consecutive days just before selected visits as outlined in the flowchart in Section 2. See (7-point profiles indicated as X and the 9-point profile indicated as ✓).

**Table 8-2 7-point SMPG profiles with additional 9-point SMPG profile**

Time point	Day -3 7-point profile	Day -2 9-point profile	Day -1 7-point profile
Before breakfast	X	✓	✓(X) a
60 minutes after the start of breakfast	X	✓	X
Before lunch	X	✓	X
60 minutes after the start of lunch	X	✓	X
Before main evening meal	X	✓	X
60 minutes after the start of main evening meal	X	✓	X
At bedtime	X	✓	X
At 4 am		✓	

aThe last SMPG in the 9-point profile and the first SMPG of the 7-point profile on day-1 are overlapping.

For 7-9-7 point SMPG measurements actual clock time, date and value should be transferred to/recorder in the diary, where each measurement should be assigned to the corresponding time point.

SMPG values measured before breakfast, lunch and main evening meal and at bedtime should be performed before any insulin injection and just before the start of the meal (breakfast, lunch or main evening meal). SMPG values measured before breakfast should be performed in a fasting condition.

The measurements will be used to evaluate the glucose profile.

### 8.3.3 Insulin dose

The subject should be instructed to report the following concerning dosing of trial products in the diary:

- Date and dose of basal and bolus insulin on the three days prior to a visit/phone contact from V2 to V26
- Date, actual clock time, and dose for other (extra) bolus insulin administration as well as time of previous main meal and reason for the extra bolus from V2 to V26 on the three days prior to a visit/phone contact.

### Dosing and dose adjustment (new dose)

The recommended insulin doses should be calculated based on the measured SMPG values as described in the Insulin Titration Guideline (see Appendix A1 and A2) for subjects with T1DM or

T2DM, respectively. At each visit/phone contact the investigator will titrate the subjects by making prescribed dose adjustments based on the recommendations described in Appendix A1 and A2 if applicable and provide the new prescribed dose to the subject.

Please refer to Appendix A for data to be collected. Information on the first and last date of trial products must be recorded in the eCRF.

## 8.4 Safety assessments

In case of an abnormal and clinically significant finding, the investigator must record the finding on the concomitant illness form if it is present at screening. Any new finding fulfilling the definition stated in Section 12 during the trial and any clinically significant worsening from baseline must be reported as an AE.

### 8.4.1 Adverse events

AEs must be reported at each visit in accordance with the procedures outlined in Section 12.

#### 8.4.1.1 Medication error

If a medication error is observed during the trial, the following information is required, and a specific event form must be completed in the eCRF in addition to the AE form:

- Trial product(s) involved
- Classification of medication error
- Whether the subject experienced any hypoglycaemic episode and/or adverse event(s) as a result of the medication error
- Suspected primary reason for the medication error

For definition of medication errors, see Section 12.1.4.

#### 8.4.1.2 Adverse events requiring additional data collection

For AEs related to injection site reaction additional data collection is required and specific event forms must be completed in the eCRF in addition to the AE form.

In case any of these events fulfil the criteria for an SAE, please report accordingly, see Section 12.

#### Injection site reaction

If an event of injection site reaction is observed the following additional information must be obtained if available on the injection site reaction form:

Protocol  
Trial ID: NN1218-4357  
UTN: U1111-1197-8289

CONFIDENTIAL

Date:  
Version:  
Status:  
Page:

30 November 2020  
5.0  
Final  
52 of 105

Novo Nordisk

- Type of reaction – local or generalised
- Symptoms associated with the event
- Treatment given for the event
- Association with the trial product(s)
- Relevant risk factors associated with the event

#### 8.4.2 Hypoglycaemic episodes

Plasma glucose (PG) should always be measured and recorded when a hypoglycaemic episode is suspected.

All PG values:

- $\leq 3.9$  mmol/L (70 mg/dL) or
- $> 3.9$  mmol/L (70 mg/dL) occurring in conjunction with hypoglycaemic symptoms

should be reported in the diary by the subject from V2 to V27 (FU1) In case a subject is not able to fill in the diary e.g. in case of a fatal event, then investigator will be allowed to report the hypoglycaemic episode in the eCRF.

Upon onset of a hypoglycaemic episode the subject is recommended to measure PG every 15 minutes until the SMPG value is  $>3.9$  mmol/L (70 mg/dL) and/or symptoms have been resolved in accordance to current guidelines.

A SMPG value  $\leq 3.9$  mmol/L (70 mg/dL) or hypoglycaemic symptoms must trigger a hypoglycaemic episode form to be completed by the subject. Repeated SMPG measurements and/or symptoms, occurring within a period of 60 min after onset on a hypoglycaemic episode, will by default be considered as one hypoglycaemic episode until a succeeding SMPG value is  $>3.9$  mmol/L (70 mg/dL) and/or symptoms have been resolved and should be reported on one hypoglycaemic episode form. SMPG measurements  $\leq 3.9$  mmol/L (70 mg/dL) or hypoglycaemic symptoms after the 60 min period shall trigger the reporting of a new hypoglycaemia episode and prompt the subject to fill out a new hypoglycaemic episode form until a succeeding measurement is  $>3.9$  mmol/L (70 mg/dL) and/or symptoms have been resolved.

In case of several low SMPG values within the 60 minutes interval, the lowest value is the one that will be reported as the SMPG value for the hypoglycaemic episode but the start time of the episode will remain as the time for the first SMPG value and/or symptom.

The record should include the following information:

- Start date and time of the hypoglycaemic episode
- The PG level before treating the episode (if available) and any follow up measurements  
The lowest value measured during the hypoglycaemic episode will be reported as the PG value for the episode, the remaining values will be kept as source data in the diary

Protocol  
Trial ID: NN1218-4357  
UTN: U1111-1197-8289

CONFIDENTIAL

Date:  
Version:  
Status:  
Page:

30 November 2020  
5.0  
Final  
53 of 105

Novo Nordisk

- Whether the episode was symptomatic (Yes/No)  
A hypoglycaemic episode starting without symptoms should be updated to symptomatic if the subject experiences symptoms later during the episode. The subject is therefore to be questioned whether there are changes to symptoms for each low SMPG value within the 60 minutes period or until the subject has confirmed that the hypoglycaemic episode is symptomatic
- Whether the subject was able to treat him/herself
- If the severity of a hypoglycaemic episode aggravates, only one hypoglycaemic episode should be reported reflecting the most severe degree of hypoglycaemia. The subject is therefore to be questioned whether he/she is able to self-treat for each low SMPG value within the 60 minutes period or until the subject respond that he/she is not able to self-treat. Date, time and dose of last bolus insulin administration prior to the episode
- Date, time and dose of last basal insulin administration prior to the episode
- Date and time of last main meal (not including snacks) prior to the episode
- Whether the episode occurred in relation to physical activity
- Change in any concomitant illness
- Any sign of fever and/or other acute disease
- Whether the subject was asleep when the episode occurred
  - If yes, whether the symptoms of the episode woke up the subject

The answer to the question: "Was the subject able to treat him/herself?" must be answered "No" for an episode requiring assistance of another person to actively administer carbohydrate, glucagon, or take other corrective actions. PG concentrations may not be available during an event, but neurological recovery following the return of PG to normal is considered sufficient evidence that the event was induced by a low PG concentration.

Oral carbohydrates must not be given if the subject is unconscious.

If the question "Was the subject able to treat him/herself?" is answered "No", the following information should be recorded by the subject:

- Who assisted in the treatment of the hypoglycaemic episode (i.e. medical person or non-medical person)?
- Where the treatment was administered (in clinic/emergency room/hospital or other. If the subject was treated in clinic/emergency room/hospital, whether they were transported in an ambulance or not)
- Type of treatment provided by another person (i.e. oral carbohydrates, glucagon, IV glucose or other)
- Were symptoms alleviated after administration of treatment?
- Factors contributing to the episode (i.e. physical activity, missed meal, diet change, medication error (i.e. overdose, mix-up between products, incorrect use of device), miscalculation of dose of antidiabetic medication, other factors not listed or unknown)

Protocol  
Trial ID: NN1218-4357  
UTN: U1111-1197-8289

CONFIDENTIAL

Date:  
Version:  
Status:  
Page:

30 November 2020  
5.0  
Final  
54 of 105

Novo Nordisk

- Did the subject experience seizure?
- Was the subject unconscious/comatose?
- Did the subject experience any of the following symptoms (layman term used in the diary is specified in brackets if different from the protocol term)?
  - Autonomic: sweating, trembling, hunger or palpitations (rapid or irregular heart beat)
  - Neuroglycopenic: confusion, drowsiness, speech difficulty, visual disturbances, odd behaviour, impaired balance or incoordination (reduced ability to coordinate movement)
  - General malaise: headache or malaise (feeling discomfort/unease)
- Other symptoms

The investigator must review the diary data for correct reporting of SMPGs and hypoglycaemic episodes. In case of incomplete or incorrect data in the diary, the subject must be questioned whether there have been any severe hypoglycaemic episodes since the last visit, i.e. any hypoglycaemic episodes where the subject was not able to self-treat. Any severe hypoglycaemic episodes must be reported.

Low SMPG values for non-severe hypoglycaemic episodes not having a hypoglycaemic episode form completed within 7 days since the SMPG measurement should be reported on a hypoglycaemic episode form with as much information as possible. Novo Nordisk will not query for additional data except for the start date, SMPG value and whether the subject was able to self-treat due to decreased validity of such data.

The subject must be re-trained in how to report hypoglycaemic episodes if the investigator identifies unreported hypoglycaemic episodes.

If the hypoglycaemic episode fulfils the criteria for an SAE then an AE form and a safety information form (SIF) must also be filled in, see Section 12. One AE form and SIF can cover several hypoglycaemic episodes if the subject has not recovered between the episodes

Protocol  
Trial ID: NN1218-4357  
UTN: U1111-1197-8289

CONFIDENTIAL

Date:  
Version:  
Status:  
Page:

30 November 2020  
5.0  
Final  
55 of 105

Novo Nordisk

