### **8.6.2 Diary**

At visit 1 the subjects will be provided with a diary to capture health issues (adverse events and changes in concomitant medication) only. At the run-in visit (V2) the subjects will be provided with a diary to capture health issues (adverse events and changes in concomitant medication), hypoglycaemia, SMPGs and dose data. The investigator must carefully instruct the subject in how to use the diary. All data entered in the diary is considered source data, as described in sections 8.3.2, 8.3.3 and 8.4.2. The recordings must be reviewed as described in Section 8.1.11 and transcribed, as applicable. Entries in the diaries are only to be made by the subject, unless otherwise specified.

Selected titration data (e.g. certain SMPGs and dose data) will only be used during the trial for central titration surveillance, to ensure compliance with the titration guideline (Appendix A1 and A2), and will not be reported in the clinical trial report (CTR). All data will be stored by Novo Nordisk (Section 24).

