### **12.2 Reporting of adverse events**

All events meeting the definition of an AE must be collected and reported. This includes events from the first trial-related activity after the subject has signed the informed consent until the end of the post-treatment follow-up period (FU2). For subjects discontinuing trial product prematurely, only SAEs should be reported between FU2 and end of trial (V26B). The events must be recorded in the applicable eCRF forms in a timely manner, see timelines below and [Figure 12-1](#).

During each contact with the trial site staff, the subject must be asked about AEs and technical complaints, for example by asking: "Have you experienced any problems since the last contact?"

All AEs, either observed by the investigator or subject, must be reported by the investigator and evaluated.

All AEs must be recorded by the investigator on an AE form. The investigator should report the diagnosis, if available. If no diagnosis is available, the investigator should record each sign and symptom as individual AEs using separate AE forms.

For SAEs, a safety information form must be completed in addition to the AE form. If several symptoms or diagnoses occur as part of the same clinical picture, one safety information form can be used to describe all the SAEs.

For all non-serious AEs, the applicable forms should be signed when the event is resolved or at the end of the trial at the latest.

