#### **HbA1c < 7.0% without severe hypoglycaemia**

A dichotomous (responder/non-responder) endpoint will be defined based on whether a subject has met the HbA1c target (HbA1c < 7.0%) 16 weeks after randomisation without treatment emergent severe hypoglycaemic episodes.

This responder endpoint will be analysed based on a logistic regression model using treatment and stratification (T1DM/T2DM) as factors and baseline HbA1c as covariate. In the analysis, subjects who prematurely discontinue trial product and subjects with missing HbA1c at 16 weeks will be included as non-responders.

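### The explicit question about severe hypoglycaemia is required only when the diary is visibly defective; asking it at every contact would be a cheap improvement in ascertainment

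*Protocol*

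**What the plan says.** Protocol section 8.4.2 sets three duties for the site:

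- Review of the diary, without condition: "The investigator must review the diary data for correct reporting of SMPGs and hypoglycaemic episodes".
- A direct question, with a condition: "In case of incomplete or incorrect data in the diary, the subject must be questioned whether there have been any severe hypoglycaemic episodes". The section explains severe here as an episode that the subject could not self-treat.
- Reporting, without condition: "Any severe hypoglycaemic episodes must be reported".

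The same section accepts that "PG concentrations may not be available during an event". It has the subject complete the episode form, and section 8.6.2 adds: "Entries in the diaries are only to be made by the subject, unless otherwise specified".

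Section 12.2 requires a general enquiry whatever the state of the diary: "During each contact with the trial site staff, the subject must be asked about AEs and technical complaints". Its example wording is "Have you experienced any problems since the last contact".

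Severe episodes enter the analysis in three places (Protocol section 17.4.1 and SAP section 4.4.1):

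- Two responder endpoints. One is HbA1c below 7.0% "16 weeks after randomisation without treatment emergent severe hypoglycaemic episodes"; the other is the matching endpoint for 1-hour PPG.
- The negative binomial analysis of severe or BG confirmed episodes.
- A separate analysis of severe episodes, if there are enough data.

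**The concern.** The condition on the direct question is a defect that the site can see. The episodes it is meant to recover need not produce one. If a relative treats the subject, nobody measures glucose and no form is filled in, the scheduled SMPG and dose entries can still all be present. The diary then gives no reason to ask.

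Comparing safety is the trial's secondary objective (section 4.1.2), and severe hypoglycaemia is the most serious category in both classifications used. Subjects with impaired awareness may take part: section 8.2.3 records awareness, and section 6.3 does not list it as an exclusion. In both responder endpoints an unrecorded episode counts as no episode.

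**Working it through.** The plan states no figure on this point, so there is nothing to reproduce. The check sets the collection rules side by side.

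**Step 1. Can a severe episode leave the diary without a visible defect?** It could show in three ways.

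- *A low glucose value.* Section 8.4.2 accepts that there may be none. The further prompt on ability to self-treat is tied to each low SMPG value, so it also needs a recorded value.
- *An episode form.* Symptoms alone are enough to require one, so a missing glucose value does not remove the duty. But the subject has to complete it.
- *A gap in scheduled entries.* Sections 8.3.2 and 8.3.3 ask for 4-point profiles and doses on the three days before each contact. An episode on another day need not leave a gap. Section 18.1 describes the 4-point profiles as daily, but four fixed times a day can also miss an episode.

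So the answer is yes. An omitted episode could be called incomplete data, but the site cannot see that omission from the diary alone.

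**Step 2. What else could bring the episode to light?**

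| Route | Needs a diary defect? | Asks about inability to self-treat? | Limit |
|---|---|---|---|
| AE question at each contact (12.2); hypoglycaemia is an AE (12.1.1) | No | Not required | Example wording is open |
| Weekly compliance check, including hypoglycaemia reporting (8.7) | No | No | Works through diary completion |
| Adding missing episode data (8.1.11) | No | No | Data must be available elsewhere |
| Investigator entry in the eCRF (8.4.2) | No | No | Investigator must know of the episode |
| Hypo/hyperglycaemia symptoms weighed in dosing (Appendices A1 and A2, section 1) | No | No | Concerns dosing decisions, not event collection |
| Hypoglycaemic episodes collected at V27 (8.1.8) | No | Not stated | One visit |
| SAE reporting (12.1.2, 12.2) | No | No | Only if SAE criteria are met; severe hypoglycaemia is not among the events always reported as SAEs |

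Several routes are open, but none is the direct question, and some work only once the episode is known.

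**Step 3. When does a missed episode change an analysis?**

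- It must be treatment emergent: onset from the first day of randomised treatment to one day after the last. An episode missed in the run-in changes no endpoint.
- For counts and rates, nothing more is needed.
- For a responder endpoint, the subject must also meet HbA1c below 7.0%, or mean 1-hour PPG of 7.8 mmol/L or less, and must not have stopped treatment early. Otherwise the subject is a non-responder anyway.
- The HbA1c change analysis does not use hypoglycaemia data.

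**Step 4. Size, as illustration only.** Assume that 2% to 5% of the 300 randomised subjects have a treatment-emergent severe episode, and that 10% to 30% of these leave no diary trace and are not found by another route.

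- Subjects with an episode: 300 × 0.02 = 6 to 300 × 0.05 = 15.
- Of these, not recorded: 6 × 0.10 = 0.6 to 15 × 0.30 = 4.5.

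Both percentages are assumptions. For the responder endpoints these results are upper bounds, because only subjects who meet the target can change status.

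**Step 5. Effect on the comparison.** If fractions u(test) and u(control) of episodes are missed, the rate ratio is multiplied by (1 − u(test)) / (1 − u(control)).

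- Equal loss, 10% or 30% in both arms: 0.90/0.90 = 1.00 and 0.70/0.70 = 1.00.
- 30% on test and 10% on control: 0.70/0.90 = 0.78.
- 10% on test and 30% on control: 0.90/0.70 = 1.29.

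Only unequal loss moves the ratio. Section 11 blinds investigator, subject and sponsor to the bolus treatment, so the equal case is the natural expectation.

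**The case against.** The strongest reply is that the protocol does not leave severe episodes to the diary alone. Adverse events are asked about at every contact, hypoglycaemia is an adverse event, and the open wording is only an example, so a site may ask more specifically. Hypoglycaemia reporting is checked weekly, episodes known from other sources must be added, and section 8.4.2 provides for retraining when unreported episodes are found. An episode that meets SAE criteria has its own forms and deadlines. The affected endpoints are supportive, and the severe-only analysis is already conditional on the data.

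Most of this stands, and it rules out several stronger readings that a reader might infer:

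- *That sites ask about hypoglycaemia only when the diary is defective.* Section 12.2 contradicts this; the condition applies only to the explicit question.
- *That only the subject can ever record an episode.* Section 8.6.2 allows exceptions, and section 8.4.2 lets the investigator enter an episode in the eCRF when the subject cannot.
- *That any missed episode turns a non-responder into a responder.* The glycaemic target must also be met on treatment.
- *That careful diary-keepers are ascertained worse, or that untraced severe episodes are the kind most often missed.* The documents show neither. A careful diary-keeper is also the subject most likely to complete the form.

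The reply does not show that the direct question is asked when the diary looks complete. No section that I could read requires that. The flowchart grid, the diary and the episode form were not available to me, so a per-visit hypoglycaemia item or a diary prompt may exist there and should be checked.

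**Conclusion.** The point holds as a limited gap in ascertainment, not as an error or contradiction. The explicit question depends on a visible diary defect, and a severe episode without a glucose value or form need not create one. The remaining prompts are general or need the episode to be known already.

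The likely consequence is some understatement of absolute severe-episode counts and, for subjects who also meet the glycaemic target, possible misclassification in two supportive responder endpoints. The number cannot be estimated from the documents; the illustrative 0.6 to 4.5 subjects rests entirely on assumed rates. Bias between arms is unlikely under blinding, and the primary HbA1c analysis is untouched. This is a cheap improvement. The conclusion assumes that the flowchart and diary contain no unconditional prompt about severe episodes.

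**What to change.** In section 8.4.2, separate the question from diary quality. For example: *At every visit and phone contact after V2, up to and including V27, the investigator must ask directly whether, since the previous contact, the subject has had any hypoglycaemic episode that he or she could not self-treat. This applies whether or not the diary is complete.* Keep the rule that severe episodes must be reported. Starting after V2 fits the diary schedule, because the diary that captures hypoglycaemia is issued at V2. If the flowchart has a hypoglycaemia row, align it with this sentence.

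The cost is one sentence and one question at contacts that already take place: V3 to V27 is 27 − 2 = 25 contacts per completing subject, if contacts are numbered consecutively. The downside is slightly more prompted reports, which blinding should keep similar between arms. The analyses need no change.
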